## Pain Control in Pediatric Oncology: Utility of EMLA Cream vs Lidocaine Injection in Lumbar Punctures

### 1. STUDY FOCUS

The focus is to compare the use of lidocaine injection versus eutectic mixture of local anesthetics consisting of 2.5% Lidocaine/Prilocaine (EMLA) cream for lumbar puncture site analgesia in pediatric oncology patients.

#### **Abstract**

A common procedure in children with cancer is the spinal tap, or lumbar puncture (LP), in which a needle is inserted into the spinal canal. In this population, LPs are most commonly performed to collect cerebrospinal fluid (CSF, the liquid surrounding the brain and spinal cord) for diagnostic testing, and to inject medications including chemotherapy. Local analgesic (pain control medicine) during pediatric LP procedures is underutilized and not standardized. The first local analgesic routinely used for LP procedures was lidocaine injection. The discovery of the topical EMLA (lidocaine 2.5%/prilocaine 2.5%) cream, approved by the FDA for local skin use in pediatric patients, has provided an additional option for local LP analgesia. A comparison between topical EMLA vs lidocaine injection for LP pain control in the pediatric population has not been performed. Pediatric oncology patients often require serial LPs for diagnostics purposes and/or chemotherapy delivery. Due to a lack of standardization of LP analgesia in this population, we have designed a prospective, single-blind, randomized control crossover trial to examine EMLA vs. lidocaine injection in reducing pain associated with LP in children being treated for leukemia or lymphoma. (Word count = 184)

#### **Specific Aims/Objectives**

Primary objective:

To compare EMLA-2.5% lidocaine/prilocaine cream versus lidocaine injection for local site analgesia for LP procedures as measured by post procedure pain scoring and PRN pain medication usage in pediatric oncology patients requiring serial LPs.

*We hypothesize that when compared, one of two examined local site analgesia strategies (EMLA or lidocaine) will provide superior pain control for LPs.*

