### **Sample**

Twenty patients will be invited to participate. A total of 17 patients are required to have a 90% percent chance of detecting a 2-point difference (standard deviation = 2.25) on the Wong-Baker Faces Pain Rating Scale (i.e. the difference from a 4 “hurts little more” to a 2 “hurts little bit”), when using paired 2-tail analysis (Wilcoxon signed-rank test). Sample size calculated

using G\*Power 3.1. We will enroll up to 20 patients to allow for patient withdrawals/loss to follow-up prior to the second LP. The accrual goal of 20 patients is comparable to other studies examining LP analgesics as well as a feasible goal with CAMC CCC's current patient load. A maximum of 50 patient records will be screened will to determine study eligibility.

*Setting:*

Charleston Area Medical Center, Women and Children's Cancer Center (CCC).

We are also inviting Pediatric Oncology at Marshall University/Cabell Huntington Hospital also to participate in the study. They will obtain approval from their local IRB. They will send de-identified study patient information to our institutions for analysis. All appropriate approvals (and data use agreements) will be obtained prior to their participation.

*Inclusion Criteria:*

- Pediatric cancer patients (aged 3-18) with a diagnosis of leukemia or lymphoma
- Patients are expected to receive serial (i.e. > 1) LP as outpatients in CCC in the course of 12 months for diagnostic and/or treatment purposes

*Exclusion Criteria:*

- Patients not in the age range
- Non-cancer patients
- Allergy to amide anesthetics
- Patients treated with class I and III anti-arrhythmic drugs (eg, amiodarone, bretylium, sotalol, dofetilide)
- Patients with congenital or idiopathic methemoglobinemia

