## **Data Analysis**

CAMC CHERI Outcome Research will perform statistical analysis for the study. Descriptive statistics will be computed. Continuous variables will be presented as means and standard deviations and if non-parametric, as medians and interquartile ranges. Categorical variables will be reported as frequencies and percentages. Each patient will serve as his or her own control; we will compare pain scores and prn medication usage for lidocaine to a patient's pain scores and prn medication usage when receiving EMLA. Tests for carryover and period effects will be conducted prior to treatment effects analyses.

Pain scores between the LPs (lidocaine vs EMLA local analgesia) will be compared using nonparametric test for matched or paired data, Wilcoxon signed-rank test. Nonparametric tests will be for statistical analyses of pain scores, as the Wong-Baker Faces Pain Rating Scale consists of ordinal values. We will analyze pain scores obtained at baseline, 30 – 60 minutes post waking after LP sedation, and 24 hours post-LP separately. Young children ( $\geq 6$  years) and children/adolescents (6-18 years) pain scale data will be analyzed jointly. In addition, if an age subgroup ( $< 6$  years or 6-18 years) has an  $n > 5$  then the age subgroup's pain scale measures will be analyzed separately.

We will analyze prn pain medication usage by comparing the amount of acetaminophen (mg/kg) reported as being taken between the two LPs local analgesics (lidocaine vs EMLA). We will compare the prn pain medication amount for each local analgesic via a paired t-test (or Wilcoxon signed-rank test if prn medication data is non-parametric). Other analgesics (if any) will be analyzed separately, in a similar manner.

A p-value of  $< 0.05$  will be used to determine statistical significance. The statistical program IBM-SPSS (Version 19) will be used for all analyses.

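### One superiority claim rests on three post-procedure tests at 0.05 each, with no primary endpoint, time point or rule for mixed results, so its error rate is not controlled

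*Combined protocol and SAP*

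**What the plan says.** Specific Aims/Objectives gives one primary objective, assessed "as measured by post procedure pain scoring and PRN pain medication usage", and one non-directional hypothesis: that "one of two examined local site analgesia strategies (EMLA or lidocaine) will provide superior pain control for LPs". Neither measure is ranked above the other.

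Data Analysis compares pain scores by the Wilcoxon signed-rank test at baseline, "minutes post waking after LP sedation, and 24 hours post-LP separately". On medication it says: "We will compare the prn pain medication amount for each local analgesic via a paired t-test", with the signed-rank test as the alternative. A p-value below 0.05 "will be used to determine statistical significance". The section contains no adjustment for multiple tests, no order of testing and no rule for combining results.

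The same section adds tests beyond these. For any age subgroup with more than five patients, the "pain scale measures will be analyzed separately". It also says: "Other analgesics (if any) will be analyzed separately, in a similar manner".

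The Sample section sizes one comparison: "A total of 17 patients are required to have a 90% percent chance of detecting a 2-point difference" on the Wong-Baker scale, with SD 2.25 and a two-tailed paired signed-rank test. It names no time point. It gives no effect size or SD for PRN use.

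**The concern.** The trial has one conclusion to draw, and the plan does not say which result would support it. At least three rules fit the text:

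1. Any one of the three post-procedure tests is enough.
2. Either pain score is enough, since only the Wong-Baker scale is used for sample size.
3. Pain and PRN use must agree, if the conjunction in the objective is taken as a requirement.

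These rules have different error rates and different power, and the choice could be made after the results are known.

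The outcomes may also conflict. The 24-hour score is taken after any medicine given at home, so lower 24-hour pain could go with higher PRN use. The plan does not say which of the two would then answer the question.

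**Working it through.** **Inputs from the documents.** Two-sided 0.05 for each test; three post-procedure tests; 2-point difference; SD 2.25; 90% power; N=17; enrolment limit 20.

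**Inputs assumed.** The documents give no correlation between outcomes, so a common correlation r from 0 to 0.95 is used. They give no score distribution, so the share of zero scores is varied. They give no PRN effect.

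**Step 1: the plan's own figure.** Read 2.25 as the SD of paired differences. The standardized effect is 2/2.25 = 0.889. Power uses the noncentral t with the signed-rank efficiency 3/π:
- effective n = 17 × 3/π = 16.2
- noncentrality = 0.889 × √16.2 = 3.58
- power = 91.7%; with 16 patients it is just under 90%

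So N=17 reproduces for one test.

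**Step 2: error if one significant result suffices.** For independent tests, three give 1 − 0.95³ = 14.3% and two give 1 − 0.95² = 9.75%. With correlation r, the error for k tests is

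1 − ∫ [Φ((z − √r·x)/√(1−r)) − Φ((−z − √r·x)/√(1−r))]^k φ(x) dx, with z = 1.96.

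| Rule (no outcome truly differs) | r=0 | r=0.5 | r=0.9 | r=0.95 |
|---|---|---|---|---|
| Any of three | 14.3% | 12.5% | 8.4% | 7.3% |
| Either pain score | 9.7% | 9.1% | 7.0% | 6.5% |

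The exact signed-rank test at n=17 has true level 4.48%. Simulated any-of-three error is then 12.7%, 11.6%, 8.1% and 6.9% at the same four correlations.

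**Step 3: the scale has six levels, with ties and a floor.** Simulation with zero differences dropped, r from 0 to 0.9, and an assumed within-patient correlation of 0.3 gives:

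| Share of scores at 0 | Any of three | Either pain score |
|---|---|---|
| 30-50% | about 9-14% | not tabulated |
| 80% | 7.6-9.9% | 5.7-6.7% |
| 85% | 5.3-6.8% | 4.0-4.6% |
| 90% | 2.4-3.2% | about 2% |

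The exact values at heavy floors depend on how the non-zero scores are spread, which is also assumed. With few non-zero differences the signed-rank test becomes conservative, and the inflation goes.

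**Step 4: error and power if pain and PRN use must agree in direction.** When no outcome differs, error is 0.2% to 4.1% for PRN use plus at least one pain score, and below 0.1% to 3.0% for all three. These are not upper limits for every case. Suppose PRN use truly differs and pain does not. At r=0 the pain side alone gives 1 − (1 − 0.0448/2)² = 4.4%, and about 4.0% after multiplying by 91% power for PRN use. Error remains below 5%.

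Power at n=17:
- One named test: 91%.
- All three: 76% (r=0) to 87% (r=0.95), if the 0.889 effect is assumed for every outcome.
- PRN use plus at least one pain score: about 90% on that assumption, but about 45% if the standardized PRN effect were 0.5. The value 0.5 is illustrative only.

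**The case against.** The best defence is that the Sample section already points to the Wong-Baker score as the lead measure, since it is the only one used for sizing. That much stands. A reader might infer from the missing primary endpoint that the trial's power is undefined or that 17 is wrong. The documents do not support this: the power of a single pain-score test is stated, and it reproduces. What remains open is which of two post-procedure time points it refers to, and what role PRN use has when the objective puts it on equal terms.

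A second defence is that the conjunction in the objective lists measures and sets no decision rule. That is fair, but it leaves the plan with no rule.

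A third is that inflation is not certain. This also stands. A reader might infer that error must exceed 5% whenever a single significant result suffices. With about 85-90% of scores at zero it may not, and the documents give no score distribution.

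A reader might also count every test in Data Analysis and put the number near ten. That count would include baseline comparisons, which cannot support a post-procedure claim. The age analyses do have a stated purpose: the Baseline Pain Level Assessment section explains that children under 6 may choose extreme faces. The count that matters for the claim is three.

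**Conclusion.** The point holds and should be fixed. The plan ties one superiority claim to three post-procedure tests at 0.05 each and gives no primary endpoint, primary time point, order or rule for mixed results. The error rate of the overall claim is therefore not controlled. If any test may count, error when nothing differs is 14.3% to 7.3% for normal outcomes, and about 9-14% on the six-level scale with 30-50% zeros. If either pain score may count, it is 9.7% to 6.5% for normal outcomes. If pain and PRN use must agree, error is below 5%, but the stated 90% power does not cover the claim.

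These sizes rest on assumed correlations and score distributions. That the deciding rule is missing rests on the text alone. N=17 is not in error for the single comparison it describes.

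**What to change.** Before any data are seen, name one Wong-Baker time point as the single primary endpoint in Specific Aims/Objectives, Sample and Data Analysis, tested by signed-rank at two-sided 0.05. The investigators should choose it. The 30-60 minute score precedes at-home medication but follows sedation; the 24-hour score follows any at-home medication. Confirm that the 2-point difference and the SD of 2.25, as the SD of paired differences, apply at that time point.

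Make the other pain time point and PRN acetaminophen secondary: either non-confirmatory, or tested in a fixed order stated in advance. Label baseline comparisons descriptive, and the age-subgroup and other-analgesic tests exploratory or sensitivity analyses.

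**Cost.** PRN use leaves the primary objective, which is a change of substance. A significant secondary result after a non-significant primary would not be confirmatory. N=17 is unchanged on the SD condition above. If 2.25 were instead the SD within each condition, N would be 30, 22, 17 or 11 for within-patient correlations of 0, 0.3, 0.5 or 0.7.

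**If PRN use must stay primary,** state that the named pain score and PRN use must both be significant in the same direction, and restate the power. At n=17 (r from 0 to 0.9) it would be 83% to 88% if the PRN effect were also 0.889, and 42% to 46% if it were 0.5; both effects are assumptions.

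**If any of the three is to count,** a Bonferroni level of 0.05/3 = 0.0167 needs 22 evaluable patients for 90% power on one test at the stated effect. Power is 88.0% at the enrolment limit of 20.

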#### **Background**

Spinal lumbar puncture (LP) is a common procedure in the pediatric patient population. They are frequently performed on emergency department and hospitalized pediatric patients, often to diagnose meningitis. To reduce pain during these procedures, local analgesics are routinely utilized. Optimal local analgesic type and method during LP procedures have been a source of disagreement for several decades, and continues to be underutilized and non-standardized, especially in pediatric patients. Studies show that analgesic use is not universal within the

pediatric population when undergoing LPs and that utilization of local anesthetic varies by patient age, with younger children less likely to receive local anesthetic. The lack of adequate analgesia may have long term consequences, with recent studies suggesting that painful experiences during infant development may alter subsequent pain pathway development and decrease pain tolerance for future procedures.

The first local anesthetic shown to be beneficial for LP procedure pain control was lidocaine injected prior to LP needle insertion. Local anesthesia with lidocaine has been shown to decrease pain in adult and pediatric populations but is often omitted with pediatric LP procedures due to concerns regarding obscuring anatomical landmarks. However, Pinheiro et al showed that local anesthesia with lidocaine decreased the degree of struggling and in the absences of lower LP success rates in newborns. Lidocaine use for local LP analgesia did not increase the number of attempts needed to obtain CSF or the number of traumatic LPs (defined as 10,000 x 10(6)/L red blood cells in CSF) in children (< 3 years old). Lastly, lack of local anesthetic use (including lidocaine) associated with increased rates of traumatic or unsuccessful LP in children and adolescents (aged 0-22 years). Thus, withholding local site analgesic for LP is unjustified.

The use of EMLA cream (lidocaine 2.5% and prilocaine 2.5%), which was approved by the United States Food and Drug Administration for local skin and genital skin use in all pediatric age groups, has provided an additional option for LP analgesia. The clinical studies supporting EMLA use demonstrated its analgesia benefits in adult IV cannulation, venipuncture, and skin graft harvesting, in pediatric patients for pre-surgical needle insertion, laser treatment of facial port-wine stains, cryotherapy for male genital wart removal, genital mucous membranes for surgical procedures, and pain control in neonates for blood drawing and circumcision procedures. EMLA has been studied in pediatric oncology patients and has shown that EMLA is associated with significantly lower pain scores and decreased indirect measures of pain (propofol doses, patient movement, and heart rate changes) when compared to placebo. In one clinical trial, the researchers examined EMLA vs. no EMLA use during repeat bone marrow biopsies and LP procedures in pediatric oncology patients. They found that EMLA was associated with decreased pain ratings for LPs, but this effect was not sustainable with repeat LP procedures. There has been concern in the past for EMLA causing a significant side effect of methemoglobinemia, although recent reports have concluded that correct usage significantly minimizes this risk.

A comparison between EMLA vs lidocaine in pediatric patients for LP-related pain to our knowledge has not been studied with the exception of needle-free injection lidocaine in neonates, which is a costly and difficult modality to deliver lidocaine. Studies in adult populations for spinal anesthesia have shown that EMLA cream is an effective alternative to lidocaine injections for analgesia with a decrease in pain scores post procedure, suggesting possible capacity to standardize LP analgesics in pediatric patients.

Pediatric oncology patients will often require serial LPs for disease progression monitoring and/or central nervous system chemoprophylaxis. Patients with leukemia or lymphoma might need up to 50 LPs throughout their 2-3 years of treatment. Topical analgesics for LP procedures are at the discretion of the oncologist and lack standardization. Currently, at Charleston Area Medical Center (CAMC), in the outpatient pediatric cancer center, oncologists use either EMLA

or lidocaine for local pain control while moderate conscious sedation is used to limit movement during the procedure. The choice of local analgesia is completely operator dependent and the same patient could receive lidocaine on some of his/her LPs and EMLA on the others. Since topical analgesics are at the discretion of the oncologist, a comparison of EMLA vs lidocaine in pediatric oncology patients undergoing serial LPs could help aid clinicians in providing safe and efficacious pain management for LPs a particularly vulnerable pediatric patient population.

## **Significance**

There is a lack of standardization regarding local site analgesia for LPs in the pediatric population. Both injected lidocaine and EMLA has been demonstrated to provide safe and effective LP local site analgesia. Therefore, comparing EMLA versus lidocaine could assist in developing a protocol to standardize care by utilizing the best analgesic for LP in children without providing futile or ineffective treatment.

## **Methodology**

### **Design**

This is a prospective, single-blinded, randomized, controlled crossover study of pediatric cancer patients receiving care at CAMC Children's Cancer Center (CCC) undergoing serial LPs as part of their management. Following study consent and assent (when required), and enrollment, patients will be randomly assigned to receive EMLA or lidocaine for local site analgesia prior to LP. The second LP post study enrollment will be defaulted to the other local site analgesic method (crossover randomization). For each LP, pain will be assessed at baseline, 30 – 60 minutes after waking up after procedure but prior to departure from the CCC, and 24 hours after procedure recorded on a home log and reported to the nurse practitioner (or other study team member) via a follow-up telephone call. Pain will be self-reported by the child using a validated pain scale. PRN pain medication use in the 24 hours following LP will also be obtained via a home log for each LP. Patient and procedure characteristics will be obtained to describe the study sample.

Patients and parents/guardians will be blinded to the randomized local site analgesic group. Since EMLA cream has to be placed prior to procedure up to a maximum of 1 hour to be effective, the patient will be awake and not sedated at that time. Therefore, sham EMLA cream will be applied to patients randomized to receive lidocaine injection. Patient will be sedated during lidocaine injection and therefore will not know if (s)he received injection. Due to their involvement in the LP procedure, it is unfeasible for the study physicians to be blinded to the randomized local analgesic.

### **Sample**

Twenty patients will be invited to participate. A total of 17 patients are required to have a 90% percent chance of detecting a 2-point difference (standard deviation = 2.25) on the Wong-Baker Faces Pain Rating Scale (i.e. the difference from a 4 “hurts little more” to a 2 “hurts little bit”), when using paired 2-tail analysis (Wilcoxon signed-rank test). Sample size calculated

using G\*Power 3.1. We will enroll up to 20 patients to allow for patient withdrawals/loss to follow-up prior to the second LP. The accrual goal of 20 patients is comparable to other studies examining LP analgesics as well as a feasible goal with CAMC CCC's current patient load. A maximum of 50 patient records will be screened will to determine study eligibility.

*Setting:*

Charleston Area Medical Center, Women and Children's Cancer Center (CCC).

We are also inviting Pediatric Oncology at Marshall University/Cabell Huntington Hospital also to participate in the study. They will obtain approval from their local IRB. They will send de-identified study patient information to our institutions for analysis. All appropriate approvals (and data use agreements) will be obtained prior to their participation.

*Inclusion Criteria:*

- Pediatric cancer patients (aged 3-18) with a diagnosis of leukemia or lymphoma
- Patients are expected to receive serial (i.e. > 1) LP as outpatients in CCC in the course of 12 months for diagnostic and/or treatment purposes

*Exclusion Criteria:*

- Patients not in the age range
- Non-cancer patients
- Allergy to amide anesthetics
- Patients treated with class I and III anti-arrhythmic drugs (eg, amiodarone, bretylium, sotalol, dofetilide)
- Patients with congenital or idiopathic methemoglobinemia

**Procedures/Protocol**

***Pre-LP***

A member of the study team will approach the pediatric cancer patient and parents/guardians (if patient is less than 18 years of age) to present and describe the study during a prescheduled visit at CAMC CCC. If the patient (and parent/guardian, if applicable) agrees to participate and signs the consent/assent, they will be enrolled in the study and be randomized to a local anesthesia arm.

*Randomization:*

A statistician from Outcome Research will prepare the randomization schedule using block randomization maintaining balance between the two treatment arms. The randomization schedule/allocation will be created using IBM-SPSS (Version 19) and completed prior to initiation of any consenting/assenting activities. A member of Outcome Research not active in enrollment will prepare sealed envelopes containing the randomized local analgesic regimen, will be prepared by a research staff member not involved in enrollment. The sealed envelopes will be maintained in the CCC to be pulled consecutively by an investigator after a patient has been consented/assented to be in the study.

Patients will be randomized to either EMLA group or lidocaine group at initial lumbar puncture post enrollment and default to the other group at the following lumbar puncture. A log will be maintained in the CCC to track enrolled patients' LPs and randomized local analgesics.

*Baseline Pain Level Assessment:*

Pain level will be measured via Wong-Baker Faces Pain Rating Scale. A numeric value is to be collected prior to LP on the day of the LP. See Appendix A for scale and directions. The Wong-Baker Faces Pain Rating Scale has been validated in children aged 3 years and older and is a pain scale that shows a series of faces ranging from a happy , "No hurt" face at 0, to a crying face at 10 "Hurts worst" with the child self-selecting (either verbally or by pointing to) the face that best describes the pain he/she is feeling.

In a systematic review, The Wong-Baker Faces Pain Rating Scale was one of only six pain scales (out of 34 pain scales) meeting criteria for a well-established pain intensity measure adequately supported by psychometric data. Children have indicated preference for the Wong-Baker FACES Pain Scale relative to other pain scales. We acknowledge the previous finding of young children (< 6 years old) sometimes selecting faces at the extremes of the scale, however it is unknown if this is related to the pain's nature or if it is a scale artifact. Due to the scale having a successful history in young children, we will use the pain scale in our enrollees (aged 3-18 years old). However, we will conduct statistical analyses for pain scale measures with and without young children (<6 years) as described in the *Data Analysis* section.

*Application of EMLA cream or Sham-EMLA cream:*

- EMLA group
  - If assigned to EMLA group, the provider will apply ~ 5 grams EMLA at least 60 minutes prior to procedure per standard protocol, covering the site with Tegaderm dressing. Studies show that Tegaderm dressing helps control dose of EMLA administered.
- Lidocaine group
  - If assigned to lidocaine group, sham-EMLA cream (Cetaphil Moisturizing Cream, a fragrance-free hypoallergenic moisturizer cream) will be applied at least 60 minutes per standard protocol with Tegaderm dressing by the provider (study nurse practitioner or physician). Cetaphil Moisturizing Cream will be used as the EMLA-sham for procedures randomized to utilize lidocaine. The Sham-EMLA cream provided by the study PI will be stored, in a secured, locked, normal room temperature area in the CCC.
  - Sham-EMLA cream will be used to reduce patient/parent reporting bias. Participants will be blinded to the type of analgesic used. The sham cream is needed because not applying any cream prior to procedure would automatically mean that the participant will receive lidocaine 1% since a local analgesic is always used.
  - Following conscious sedation, the patient will receive lidocaine 1% injection (~1-2ml) at the appropriate site 30-60 seconds prior to LP needle insertion.

- In order to maintain patient blinding, the sham-EMLA container or the EMLA tube kept out of sight of patient. We will put the cream on the Tegaderm bandage and then put it on the patient's back.
- The pain medicine (lidocaine 1% and EMLA) are standard for LP associated pain regardless of the study. The pain medicines will be provided by CAMC Pharmacy and secured in the MedStation in the CCC following same processes as non-study LPs.

